#### **10.4.1.3 Adverse event of special interest**

An adverse event of special interest (AESI) is an AE (serious or non-serious) that needs to be monitored, documented, and managed in a pre-specified manner described in the protocol.

For this study, the AESIs are the following (refer also to [Section 10.4.4](#) for the reporting time frame, and the corresponding complementary forms in the e-CRF to be filled):

- **Increase in alanine aminotransferase (ALT):**
  - ALT  $\geq 3 \times$  ULN (if baseline ALT  $<$ ULN) or ALT  $\geq 2$  times the baseline value (if baseline ALT  $\geq$ ULN) (Please refer to related flowchart in [Appendix F](#)).
- **Allergic events that require consultation with another physician** for further evaluation of hypersensitivity/allergy as per the Investigator's medical judgment.
- **Local injection site reactions that are allergic in nature:**
  - Local injection site reactions deemed to be allergic by the Investigator (or have an allergic component) and that require consultation with another physician for further evaluation of hypersensitivity/allergy as per the Investigator's medical judgment should be reported as AESIs.

Note: Other local injection site reactions are non-AESIs. Please see [Section 10.4.1.4](#) for details.

Note: The safety instructions on allergic events and local injection site reactions are detailed in [Section 10.6](#).
- **Pregnancy:**
  - Pregnancy occurring in a female patient or the female partner of a male patient (if data collection is permitted by the female partner and by local regulatory authorities) during the study or within 70 days (10 weeks) following the last dose of IMP.
  - Pregnancy will be recorded as AESI in all cases. Pregnancy will be qualified as an SAE only if it fulfils one or more SAE criteria.
  - In the event of pregnancy of a female patient included in the study, the IMP should be permanently discontinued.
  - The follow-up of the pregnancy will be mandatory until the outcome is determined.
- **Symptomatic overdose with IMP:**

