### **10.6.3 Allergic adverse event with cutaneous involvement**

Adverse events with cutaneous involvement which are obviously of allergic origin or injection site reactions which progress/expand/worsen/etc. should be evaluated by a dermatologist as soon as possible, and preferably within one week of the site first becoming aware of the event.

The Investigator should evaluate the patient for possible etiologies (new medications, etc.) and extracutaneous symptoms and signs. An unscheduled Local Laboratory assessment for hematology, chemistry, liver panel should be obtained. If it is possible, the site will take pictures of the skin lesions in order to provide the patient with them for the dermatologist's visit. If the photos are obtained, then copies should be kept as source documents which may later be collected by the sponsor. The Investigator will provide a summary of the patient's case, reason for consultation, and information being requested to the consulting dermatologist.

A full consultation report should be sent by the dermatologist to the Investigator. The full report should contain, at a minimum, the following information; a detailed description of the rash (such as the morphology [lesion type], shape of individual lesions, arrangement of multiple lesions [eg, scattered, grouped, linear], distribution, color, consistency, presence of pruritus or pain, and other clinical signs) and in case a skin biopsy (including histopathology and immunofluorescence) was done (if it was deemed necessary as per the dermatologist's or Investigator's medical judgment), the results of this investigation with, if applicable, a specific diagnosis of the AE. The Investigator will fax the full report and the corrected AE form if necessary, to the Monitoring Team Representative within 24 hours.

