## Appendix H Assessment of Local Injection Site Reactions

Local, Non- Allergic Reaction to Injectable Product	Mild (Grade 1)	Moderate (Grade 2)	Severe (Grade 3)	Very Severe (Grade 4)
Pain	Does not interfere with activity	Interferes with activity or repeated use of non-narcotic pain reliever	Prevents daily activity or repeated use of narcotic pain reliever	Emergency Room (ER) visit or hospitalization
Tenderness	Mild pain to touch	Pain with movement	Significant pain at rest	ER visit or hospitalization
Erythema / Redness *	2.5 – 5 cm	5.1 – 10 cm	>10 cm	Necrosis or exfoliative dermatitis
Swelling **	2.5 – 5 cm and does not interfere with activity	5.1 – 10 cm or interferes with activity	>10 cm or prevents daily activity	Necrosis
Itching	Does not interfere with activity	Interferes with activity or repeated use of topical or systemic treatment	Prevents daily activity or leads to other significant dermatologic conditions (such as infection, scarring, etc.)	Emergency Room (ER) visit or hospitalization
Other (Please specify)***	No modification of daily activities and/or does not require symptomatic treatment.	Hinders normal daily activities and/or requires symptomatic treatment.	Prevents daily activities and requires symptomatic treatment.	Emergency Room (ER) visit or hospitalization

\* In addition to grading the measured local reaction at the greatest single diameter, the measurement should be recorded as a continuous variable.

\*\* Swelling should be evaluated and graded using the functional scale as well as the actual measurement.

\*\*\* Please specify the other signs or symptoms (for example, hematoma, discoloration, reactivation, etc.).

ADAPTED from the toxicity grading scale table from the FDA Draft Guidance for Industry: Toxicity Grading Scale for Healthy Adult and Adolescent Volunteers Enrolled in Preventive Vaccine Clinical Trials April 2005.

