### ***Adverse events of special interest***

An AESI is an AE (serious or non-serious) that needs to be monitored, documented, and managed in a pre-specified manner described in the protocol.

Following an amendment to the initial protocol (See [Section 1.5](#)), the AESIs will be analyzed according to the amended protocol.

For this study, the AESIs are the following:

- Increase in alanine aminotransferase (ALT): ALT  $\geq 3 \times$  upper limit of normal range (ULN) (if baseline ALT  $<$ ULN) or ALT  $\geq 2$  times the baseline value (if baseline ALT  $\geq$ ULN), selected using laboratory data (see Appendix F in the protocol).
- **Allergic events that require consultation with another physician** will be described. Events will be selected using the following standardized MedDRA query (SMQ): “hypersensitivity” (broad and narrow) excluding the preferred terms linked to local injection site reactions (“infusion site dermatitis”, “infusion site hypersensitivity”, “infusion site rash”, “injection site dermatitis”, “injection site hypersensitivity”, and “injection site rash”). The condition “consultation with another physician” will be considered as verified if a dermatology consultation was completed and/or if a description of the rash was provided by the dermatology consultation.
- In addition, an analysis will be performed for any allergic event whether meeting or not AESI criteria meeting the above SMQ criteria.
- **Local injection site reactions that are allergic in nature** deemed to be allergic by the Investigator (or have an allergic component) AND that require consultation with another physician will be selected using the PTs corresponding to local allergic reactions: “Injection site dermatitis”, “Injection site hypersensitivity”, “Injection site oedema”, “Injection site rash”, “Injection site urticaria”, “Injection site eczema”, “Injection site vasculitis”, “Injection site swelling”, “Infusion site dermatitis”, “Infusion site hypersensitivity”, “Infusion site oedema”, “Infusion site rash”, “Infusion site urticaria”, “Infusion site swelling”. The condition “consultation with another physician” will be considered as verified if a dermatology consultation was completed and/or if a description of the rash was provided by the dermatology consultation.
- An analysis using these PTs will also be performed for any local injection site reaction whether requiring consultation or not.

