- In addition, an analysis will be performed for any local injection site reaction not meeting AESI criteria (not allergic and not requiring consultation with another physician) using the HLT “injection site reaction”.
- **Pregnancy** of female patients will be selected using the appropriate MedDRA codes.

- **Symptomatic overdose with Alirocumab.** Overdose with alirocumab is defined as at least twice of the intended dose within the intended therapeutic interval (ie, 2 or more injections are administered in <7 calendar days), to be reported using the Term “symptomatic OVERDOSE” (accidental or intentional), indicating the circumstance in parentheses (eg, “symptomatic overdose [accidental]” or “symptomatic overdose [intentional]”). These events will be selected using the AESI category as selected by the site.
- Another analysis will be performed using all overdose cases (whether symptomatic or asymptomatic and whether with alirocumab or another drug) using the HLT “Overdose”.
- In addition, an analysis will be performed using all overdose cases (whether symptomatic or asymptomatic) using the HLT “Overdose” with the condition “relationship to investigational medicinal product (IMP)” as YES.
- **Neurologic events that require additional examinations/procedures and/or referral to a specialist** will be selected using SMQ “demyelination” (broad and narrow), “peripheral neuropathy” (broad and narrow), and “Guillain Barre syndrome” (broad and narrow) excluding the following preferred terms: “acute respiratory distress syndrome”, “asthenia”, “respiratory arrest”, and “respiratory failure”.
- An additional analysis will be performed analyzing all events meeting the above SMQ criteria for neurologic events whether or not the criteria for an AESI are met (whether or not requiring additional exams/procedures and/or referral to a specialist).
- **Neurocognitive events** will be selected using the sponsor Company MedDRA Query (CMQ) based on HLTs “Deliria (incl confusion)”, “Cognitive and attention disorders and disturbances”, “Dementia and amnestic conditions”, “Disturbances in thinking and perception”, “Mental impairment disorders”.

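### The SAP selects allergic injection-site AESIs by a closed term list and a dermatology visit, so reactions that meet the protocol definition can be left out of the AESI analyses

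*SAP*

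**What the plan says.** **Definition.** Protocol 10.4.1.3 makes these events AESIs: "Local injection site reactions deemed to be allergic by the Investigator (or have an allergic component) and that require consultation with another physician". The specialty of the other physician is not restricted.

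**Selection.** SAP 2.1.4.1 says AESIs will follow the amended protocol and restates both conditions in its selection sentence: "deemed to be allergic by the Investigator (or have an allergic component) AND that require consultation with another physician will be selected using the PTs". It then lists 14 of them:

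- eight injection-site terms: dermatitis, hypersensitivity, oedema, rash, urticaria, eczema, vasculitis and swelling;
- six infusion-site terms: the same set without eczema and vasculitis.

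The consultation condition "will be considered as verified if a dermatology consultation was completed and/or if a description of the rash was provided by the dermatology consultation". There is no matching rule for the Investigator's allergic judgement.

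**Related analyses.** The SAP adds an analysis of the same terms regardless of consultation. It also adds one using the high-level term for injection site reactions, limited to reactions that are not AESIs, which it describes as neither allergic nor referred. For symptomatic overdose it takes another route: "These events will be selected using the AESI category as selected by the site".

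**Use.** SAP 2.4.5.1 builds the AESI tables from these selections. It also plans Kaplan-Meier curves, when appropriate, and 24-week incidences for all AESIs.

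**The concern.** The protocol defines the event by a clinical judgement. The SAP finds it by how the event was coded and which specialist saw it. These are different inputs and need not pick the same patients.

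AESIs belong to the primary safety endpoint, and Protocol 9.1 ties tolerability to local injection site reactions. If the selected set differs from the defined set, the allergic injection-site row and its time-to-event summaries will carry the protocol's label but describe something else. They may also disagree with the AESIs that sites had to report within 24 hours under Protocol 10.4.4.

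**Working it through.** No arithmetic decides this point, so the check compares the two rules condition by condition.

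**Inputs**

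- A: the Investigator judges the reaction allergic or partly allergic (Protocol 10.4.1.3).
- C: consultation with another physician, of any specialty, is required (Protocol 10.4.1.3).
- L: the coded term is one of the 14 (SAP 2.1.4.1).
- D: a dermatology consultation was completed, or it supplied a rash description (SAP 2.1.4.1).

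The protocol rule is A and C. The SAP sentence allows two readings. In reading 1 the terms stand in for the judgement, so the rule is L and D. In reading 2 the judgement remains a filter, so the rule is A and L and D.

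| Case | Protocol | Reading 1 | Reading 2 |
|---|---|---|---|
| 1. Judged allergic, referred, coded as rash, dermatologist seen | AESI | selected | selected |
| 2. Judged allergic, referred, coded as redness or itching, dermatologist seen | AESI | missed | missed |
| 3. Judged allergic, coded as rash, seen only by a non-dermatologist | AESI | missed | missed |
| 4. Judged non-allergic, coded as swelling, dermatologist seen | not AESI | selected | not selected |

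**Cases 2 and 3** fail under both readings. Redness and itching are injection-site signs graded in Protocol Appendix H, and neither has a matching term on the list. Case 3 fails because the SAP narrows any other physician to a dermatologist.

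**Case 4** arises only under reading 1. It is possible because the list includes the non-specific terms "Injection site swelling" and oedema, and because Protocol 10.6.3 says that "injection site reactions which progress/expand/worsen/etc. should be evaluated by a dermatologist as soon as possible". Protocol 10.6.2 points to that section for worsening reactions just after discussing events that are clearly not allergic.

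**Do the added analyses recover cases 2 and 3?** The analysis regardless of consultation uses the same 14 terms, so it recovers case 3 but not case 2. The high-level-term analysis, taken at its word, excludes reactions that were allergic and referred. If it were run as everything not selected, it would show them as non-AESI.

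**Scale only.** The plan's rule-of-three figure reproduces: 3/1300 = 0.231%, or 1 per 433. One patient is 1/1300 = 0.077%, so three misclassified patients equal that limit. This is not an estimate of how many there will be.

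**The case against.** The strongest reply has five parts.

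1. **The sentence does name the Investigator's judgement.** Its grammatical subject is reactions judged allergic and referred, and the terms may only say how to find them. This stands for case 4. A reader might infer that the rule necessarily counts non-allergic swelling, or that every worsening swelling sent to a dermatologist becomes a false AESI. The documents do not support that. Reading 2 removes such cases, and a referred swelling that the Investigator judged allergic is a true AESI. Protocol 10.6.2 itself lists injection-site swelling among possibly allergic events. Appendix H, although headed "Local, Non- Allergic Reaction to Injectable Product", is a severity scale and not a rule for assigning cause.

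2. **The protocol pushes towards agreement.** Section 10.4.2 prefers a diagnosis to symptoms, so some allergic reactions will be reported in words that code to a listed term. Section 10.6.3 asks for a dermatologist when a skin event is obviously allergic. Both make cases 2 and 3 less frequent; neither rules them out.

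3. **Nothing disappears from safety reporting.** All TEAEs are tabulated by preferred term, and symptoms of general allergic reactions are listed. The hypersensitivity query used for the allergic-event AESI might catch some off-list reactions, but its contents are not in the documents. This limits the harm but does not correct the AESI row.

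4. **Term-based selection is uniform across sites** and is used for other AESIs. That is a good reason to keep the term search as a second analysis.

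5. **Site categories have weaknesses too.** SAP 1.5 records that the AESI list changed in an amendment approved on 01 March 2016, after the first enrolment on 08 July 2015. Entries made before then may follow the old list. This is a fair point, and the fix has to deal with it.

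**Conclusion.** The point holds for omissions. As written, a reaction that meets the protocol definition is left out of this AESI's table, curves and 24-week incidence if it is coded off the 14-term list or lacks a dermatology consultation. This is so under either reading of the sentence. Over-counting of non-allergic swelling or oedema is conditional: it occurs only if the Investigator's judgement is not programmed as a filter, and the SAP names no variable for it.

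The size cannot be estimated. The documents give no rate of allergic injection-site reactions for this trial, no share coded off the list and no split of referrals by specialty. Any count would only restate assumed rates. The study is descriptive and the events remain in the general TEAE tables, so no test result is affected and no event is lost from safety reporting. The change should still be made, because this row reports part of the primary endpoint and, with few events, one or two misclassified patients would matter proportionally. The conclusion assumes that redness and itching are coded to terms outside the list, which follows from the list as printed.

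**What to change.** In SAP 2.1.4.1, replace the selection rule for this AESI with wording such as:

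> Allergic local injection site reactions meeting the AESI definition will be identified by the AESI category recorded by the site. Consultation with any other physician counts. The 14 preferred terms will be used for a supportive analysis, labelled as a term search. Cases where the two selections disagree will be listed, marking those entered before the amendment that changed the AESI list.

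Use the site-recorded set for the AESI table, the Kaplan-Meier curves and the 24-week incidence. Keep the planned analysis of the 14 terms regardless of consultation.

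The cost is a few sentences of SAP text, one changed selection flag and one listing, with no protocol amendment. New data should not be needed: the overdose rule already relies on a site-selected category, and Protocol 10.4.4 and Appendix E require sites to report these reactions as AESIs on dedicated forms. The case report form is not among the documents, so confirm before database lock that the category was recorded for injection-site reactions. The downside is reliance on site classification, which the retained term search and the discordance listing cross-check.

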## 9 ASSESSMENT OF INVESTIGATIONAL MEDICINAL PRODUCT

### 9.1 PRIMARY ENDPOINTS

In this study, primary endpoints only relate to safety assessments.

Safety will be assessed throughout the study by the following parameters:

- Recording of adverse events (including serious adverse events and adverse events of special interest).
- Standard laboratory tests: hematology (hemoglobin, WBC, platelet count) and biochemistry (urea, creatinine, glucose, glycated hemoglobin A1c [HbA1c], total CK).
- Liver function tests: SGOT (AST), SGPT (ALT), alkaline phosphatase (ALP), total bilirubin.
- Physical examination and vital signs: height (only at screening), weight, heart rate, systolic and diastolic blood pressure
- Device related complaints will be recorded and described as well.

Reporting procedures for AEs, SAEs and AESI are detailed in [Section 10.4](#), [Section 10.5](#), [Section 10.6](#), [Section 10.7](#).

The assessment of tolerability refers to local injection site reactions (see [Appendix H](#)).

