#### **10.4.1.4 Local injection site reactions (non-allergic or allergic not requiring consultation)**

Local injection site reactions that are considered non-allergic (eg, local injection site reactions related to mechanics of injection) or allergic but not requiring consultation with another physician are not considered as AESIs.

The definition of local injection site reactions, the reporting time frame, and the corresponding complementary forms in the e-CRF to be filled are summarized in [Appendix E](#).

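### The SAP's wording for non-AESI injection site reactions is not the complement of its AESI definition, so read literally it leaves some reactions out of every dedicated injection-site set

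*SAP*

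**What the plan says.** SAP 2.1.4.1 (Adverse events of special interest) sets up three analyses of local injection site reactions.

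- **AESI set.** Reactions "deemed to be allergic by the Investigator (or have an allergic component) AND that require consultation with another physician". In practice these "will be selected using the PTs corresponding to local allergic reactions", a list of 14 terms. The consultation condition "will be considered as verified if a dermatology consultation was completed", or if that consultation supplied a description of the rash.
- **Listed-term set.** "An analysis using these PTs will also be performed for any local injection site reaction whether requiring consultation or not".
- **Non-AESI set.** Reactions under the HLT for injection site reactions that do not meet the AESI criteria, with the explanation "not allergic and not requiring consultation with another physician".

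Protocol 10.4.1.4 draws the line differently. It says that reactions considered non-allergic, "or allergic but not requiring consultation with another physician are not considered as AESIs". A note in protocol 10.4.1.3 likewise treats every other local reaction as non-AESI, and Appendix E repeats this.

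**The concern.** The AESI needs two conditions together, so a reaction escapes it by failing either one. The parenthesis admits only reactions that fail both. It therefore disagrees with the clause it explains, and with the protocol that the SAP says governs the AESI analysis.

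The omitted combinations can occur. Protocol 10.6.2 takes up reactions that are plainly not allergic, such as those due to the mechanics of injection, and sends them on to 10.6.3 if they get worse. Section 10.6.3 says that "injection site reactions which progress/expand/worsen/etc. should be evaluated by a dermatologist", as an alternative to being obviously allergic. A completed dermatology consultation is also the SAP's marker for consultation.

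The topic belongs to the primary objective. Protocol 9.1 states that "The assessment of tolerability refers to local injection site reactions". A pre-specified safety table in this area should have a selection rule that can be programmed in only one way.

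**Working it through.** No sample size, rate or interval in the plan bears on this, so there is no figure to reproduce. The check is a truth table.

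**Inputs.** A = the investigator calls the reaction allergic. L = its preferred term is on the SAP's list of 14. C = a dermatology consultation was completed.

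**Rules.**
- Protocol: AESI = A and C. Non-AESI = everything else, that is, not A or not C.
- SAP AESI set: L and C. On a stricter reading, A as well.
- SAP listed-term set: L.
- SAP non-AESI set, by the parenthesis: not allergic and not C. *Allergic* can mean A (the investigator's view) or L (a listed term). Both are shown.

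| Row | A | L | C | Protocol status | SAP AESI | Listed-term | Non-AESI, allergic = A | Non-AESI, allergic = L | In none of the three sets |
|---|---|---|---|---|---|---|---|---|---|
| 1 | yes | yes | yes | AESI | yes | yes | no | no | |
| 2 | yes | yes | no | non-AESI | no | yes | no | no | |
| 3 | yes | no | yes | AESI | no | no | no | no | either reading |
| 4 | yes | no | no | non-AESI | no | no | no | yes | if allergic = A |
| 5 | no | yes | yes | non-AESI | yes, or no if A also required | yes | no | no | |
| 6 | no | yes | no | non-AESI | no | yes | yes | no | |
| 7 | no | no | yes | non-AESI | no | no | no | no | either reading |
| 8 | no | no | no | non-AESI | no | no | yes | yes | |

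**Results.**
- Rows 3 and 7 (unlisted term, dermatology consultation) fall in none of the three sets on either reading.
- Row 4 (called allergic, unlisted term, no consultation) falls in none if *allergic* means the investigator's view.
- Rows 2 and 5 always miss the non-AESI set, although the protocol calls them non-AESI, and row 6 misses it if *allergic* means a listed term. The listed-term analysis still captures all three.

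Unlisted terms are not rare in kind. Of the five named symptoms graded in protocol Appendix H (pain, tenderness, erythema, swelling, itching), only swelling appears by name on the SAP list.

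**With the true complement.** Not (allergic and C) = not allergic or not C. Taking *allergic* as L on both sides, rows 1 and 5 are AESI and rows 2, 3, 4, 6, 7 and 8 are non-AESI. Each row falls in exactly one set. If L selects the AESI set while A defines the non-AESI set, row 3 is still in neither, so the marker must be the same on both sides.

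**The case against.** The main clause already describes the right set, and the SAP says AESIs follow the amended protocol, which has the correct definition. A programmer who follows either would include every reaction. That is fair: this is a contradiction inside one sentence, and events are lost only if the parenthesis is taken as the rule. It still needs correcting, because nothing says which part prevails.

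A reader might infer that tolerability as a whole would be undercounted. The documents do not support that. SAP 2.4.5.1 reports all TEAEs by HLT and preferred term, by maximal severity, by relationship and per patient-year in the whole safety population. The same section tabulates intensity, events per injection, time to first reaction and symptoms for local injection site reaction TEAEs, with no allergic or consultation restriction. The one loose end is that this passage sits under the AESI heading, straight after a reference to the 2.1.4.1 selections, so it could be built from those sets.

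A reader might also infer that the omitted reactions are the more severe ones, since worsening reactions go to a dermatologist. That is plausible but not shown. Section 10.6.3 is headed as concerning allergic events, and reactions that worsen also need the general allergic form. Many may therefore be judged to have an allergic component. Worsening swelling or rash would be caught by the listed terms.

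**Conclusion.** The parenthesis is wrong as written. It contradicts its own main clause and protocol 10.4.1.3, 10.4.1.4 and Appendix E. Applied literally, it drops from the dedicated sets unlisted-term reactions with a dermatology consultation and, if allergic means the investigator's judgement, unlisted-term allergic reactions without one.

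The effect is confined to the AESI/non-AESI breakdown, which is descriptive. Total reporting of injection site reactions stands, on the assumption that the 2.4.5.1 tabulations are run as worded, on all such reactions. The documents give no expected rate of injection site reactions or of dermatology referral, so the number of events affected cannot be computed, and any percentage would be an assumption.

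**What to change.** In SAP 2.1.4.1, change the parenthesis to *not allergic or not requiring consultation*, or delete it and let the main clause stand. Say which marker defines allergic (the listed terms or the investigator's judgement) and use it for both sets, so that every reaction under the HLT falls in exactly one of them. Optionally, add a sentence to SAP 2.4.5.1 confirming that the intensity, per-injection, time-to-first and symptom tabulations cover all local injection site reaction TEAEs.

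The cost is one word and one or two clarifying sentences before programming. No new data or additional analyses are needed.

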##### Death observation period:

The death observations are per the observation period defined above. In addition, “post- study” death includes all deaths reported after the end of the study (see definition of end of study period per patient in [Section 6.2.1](#)).

Adverse events, including AESIs and SAEs, will be collected from the time the patient signs the informed consent to the completion of the safety observation period.

All AEs will be coded to a “lowest level term (LLT)”, “preferred term (PT)”, “high level term (HLT)”, “high level group term (HLGT)” and associated primary “system organ class (SOC)” using the version of Medical Dictionary for Regulatory Activities (MedDRA) currently in effect at Sanofi at the time of the considered database lock.

Adverse events of special interest may be modified during a study by protocol amendment, which will enable the Company to collect additional information to better assess any potential and identified risks during the development.

For this study, the following AEs are AESI:

- Increase in alanine transaminase (ALT): ALT  $\geq 3 \times$  ULN (if baseline ALT  $<$  ULN) or ALT  $\geq 2$  times the baseline value (if baseline ALT  $\geq$  ULN).
- Allergic events and/or local injection site reaction that are allergic in nature and that require consultation with another physician for further evaluation.
- Pregnancy.
- Symptomatic overdose with IMP.
- Neurologic events that require additional examinations/procedures and/or referral to a specialist.
- Neurocognitive events.

Additional information can be found in [Section 10.4.1.3](#) and [Appendix E](#).

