  - An overdose (accidental or intentional) is an event suspected by the Investigator or spontaneously notified by the patient (not based on systematic injection counts) and defined as at least twice of the intended dose within the intended therapeutic interval (ie, 2 or more injections of the study treatment are administered in  $<7$  calendar days). The symptomatic overdose should be reported using the term "symptomatic overdose (accidental or intentional)", indicating the circumstance in parentheses (eg, "symptomatic overdose [accidental]" or "symptomatic overdose [intentional]"). The patient should be monitored and appropriate symptomatic treatment instituted,
  - The circumstances of the overdose should be clearly specified in the verbatim, and the symptoms, if any, entered on separate AE/SAE forms,
  - Of note, asymptomatic overdose should be reported as a standard AE.

- **Neurologic events:**
  - Neurologic events that require additional examinations/procedures and/or referral to a specialist should be reported as an AESI. If the event does not require additional examinations/procedures and/or referral to a specialist, it should be reported as a standard adverse event.
- **Neurocognitive events:**
  - All neurocognitive events will be considered as AESI.

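### The SAP's query for neurologic AESIs is narrower than the protocol definition, and its work-up/referral condition has no verification rule

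*SAP*

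**What the plan says.** Protocol 10.4.1.3 gives the definition that sites apply: "Neurologic events that require additional examinations/procedures and/or referral to a specialist should be reported as an AESI". Section 9.1.1 lists the same category with no limit by type of event. Section 10.4.4 and Appendix E require these events to be notified within 24 hours, with the AE form, the safety complementary form and other specific forms. Section 11.4.2.1 promises an incidence table of all treatment-emergent AESIs.

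SAP 2.1.4.1 states that "the AESIs will be analyzed according to the amended protocol". It then names the neurologic AESI in the protocol's terms but selects events through three SMQs, each in broad and narrow scope, and removes four preferred terms. A further analysis drops the work-up/referral condition but covers only "An additional analysis will be performed analyzing all events meeting the above SMQ criteria for neurologic events".

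For symptomatic overdose the SAP takes a different route: "These events will be selected using the AESI category as selected by the site".

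**The concern.** Sites apply an open definition and the analysis applies a closed list. A neurologic event that a site judged to be an AESI and expedited within 24 hours can fail to appear as an AESI in the study report. AESIs are one of the safety parameters that make up the primary endpoint. The study is single-arm and descriptive, so the tabulated incidence is itself the result, with no comparison behind it. An AESI table that does not reconcile with the AESIs collected would be hard to interpret.

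There is a second gap. The SAP does not say how a programmer should establish that an event needed further work-up or referral, although that condition separates a neurologic AESI from an ordinary neurologic AE.

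**Working it through.** The plan states no figure on this point, so the check is mainly a comparison of texts.

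1. **Definition.** Protocol 9.1.1 and 10.4.1.3 set one condition: a neurologic event that needs further work-up or referral. Neither restricts the event by term or query.

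2. **Selection.** SAP 2.1.4.1 adds a second condition: the term must lie in one of three SMQs and must not be one of four excluded preferred terms. The selected set can therefore be no larger than the protocol's set, and it is smaller whenever a qualifying event lies outside the SMQs.

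3. **Fallback.** The additional analysis removes the first condition and keeps the second. It widens the set inside the SMQs and recovers nothing outside them.

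4. **Outputs affected.** SAP 2.4.5.1 builds the AESI summaries from the selections in 2.1.4.1. It also defines the Kaplan-Meier set as all AESIs in that section. Both inherit the filter.

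5. **Outputs not affected.** The same section tabulates all TEAEs by SOC and preferred term, by relationship, by severity and per patient-year. It also tabulates serious TEAEs and TEAEs leading to discontinuation. A missed neurologic AESI stays in whichever of these applies. None of them carries the work-up/referral condition, so they cannot give the incidence of neurologic AESIs.

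6. **Partial overlap.** Neurocognitive events have their own queries in 2.1.4.1: a set of HLTs, and a second list based on an FDA grouping. A neurologic event caught there appears as a neurocognitive AESI. The events missed are those outside both the three SMQs and these queries.

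7. **The condition.** For allergic events and allergic injection site reactions, the SAP treats consultation as verified when a dermatology consultation was completed or supplied a description of the rash. For overdose it relies on the site's category. For neurologic events it gives no rule. If the condition is ignored, the AESI selection coincides with the additional analysis. If it is applied, the rule has to be invented after the fact.

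8. **Disclosure.** SAP 1.5 lists changes to the statistical section and 1.6 is marked not applicable. Neither mentions the restriction to three SMQs.

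**Size, by assumption only.** Expected patients missing = N × p × (1 − s). N = 1300 is the target sample size. The rate p of protocol-defined neurologic AESIs and the share s captured by the planned AESI queries are both assumed.

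| p | Patients with an AESI (1300 × p) | Missing, s = 75% | Missing, s = 50% | Missing, s = 25% |
|---|---|---|---|---|
| 1% | 13 | 3.25 | 6.5 | 9.75 |
| 2% | 26 | 6.5 | 13 | 19.5 |
| 4% | 52 | 13 | 26 | 39 |

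If s is 100%, none are missing. The table shows how the shortfall scales and is not an estimate.

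**The case against.** Selection by coded terms is the SAP's usual method. It uses an SMQ for allergic events, a list of preferred terms for local reactions, MedDRA codes for pregnancy and company queries for neurocognitive events. Only symptomatic overdose uses the site's category. A query applies one rule to every patient, and broad-and-narrow scope is not the tightest choice. The AESI list was also modified by an amendment approved on 01 March 2016, after the first patient was enrolled on 08 July 2015, so site categories may reflect two lists. The SAP's statement about the amended protocol is best read as saying which list applies, not as a promise to use the site flag. All of this stands, and it is a good reason not to discard the SMQ analysis. It does not make three queries equal to an open definition, and it does not supply the missing verification rule.

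A reader might infer that the omitted events disappear from the report, or that no neurologic AESI outside the SMQs can reach any AESI output. The documents do not support either reading. The general TEAE, SAE and discontinuation tables keep the events, and the neurocognitive queries would catch some of them. Expedited reporting is also unaffected.

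It is stated only for overdose that a site-selected category exists. For neurologic events it is a reasonable inference from the forms required in Appendix E.

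**Conclusion.** Wrong as written. The neurologic AESI selection in SAP 2.1.4.1 is narrower than the protocol's definition, and the work-up/referral condition cannot be applied as specified. The effect is confined to the AESI table and the AESI Kaplan-Meier analysis. It concerns neurologic AESIs that lie outside both the three SMQs and the neurocognitive queries.

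The mismatch follows from the wording and rests on no assumed rate. Its size cannot be estimated from the documents and may be small. It would also be too strong to say that the primary endpoint as a whole is misreported. AESIs are one of several safety parameters, all described without formal testing, and the events stay visible elsewhere. The point is still worth correcting, because the protocol promised a table of all treatment-emergent AESIs and the planned one would not deliver it for this category.

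**What to change.** In SAP 2.1.4.1 and 2.4.5.1:

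- Add to the AESI table and the Kaplan-Meier set a neurologic AESI analysis based on the AESI category selected by the site, as is already done for symptomatic overdose.
- State that the work-up/referral condition is verified from that category or from the neurologic AESI forms required by Protocol Appendix E.
- Keep the three-SMQ grouping as a parallel standardised analysis, with its four exclusions.
- Footnote that site categories may have been assigned under two versions of the AESI list. The documents do not say which entries changed.

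The cost is one extra table, a sentence or two of SAP text and a matching addition to the Kaplan-Meier output. No new data should be needed, provided that the eCRF category or the specific forms identify neurologic AESIs. This should be confirmed before database lock.
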